4.6. Safety Variables

4.6.1. Adverse Events and Serious Adverse Events

An Adverse Event (AE) is any untoward medical occurrence in a patient administered a study drug which may or may not have a causal relationship with the study drug. Therefore, an AE is any unfavorable and unintended sign (including abnormal laboratory finding), symptom, or disease which is temporally associated with the use of a study drug, whether or not considered related to be study (ICH E2A Guideline).

A Serious Adverse Event (SAE) either results in death, is life-threatening, requires in-patient hospitalization or prolongation of existing hospitalization, results in persistent or significant disability/incapacity, congenital anomaly/birth defect, or is an important medical event. The protocol provides the details.

Treatment-emergent adverse events (TEAEs) are defined as those that are not present at baseline or represent the exacerbation of a pre-existing condition during the observation period.

4.6.2. Adverse Events of Special Interest

Adverse events of special interest (AESI) are AEs (serious or non-serious) required to be monitored, documented, and managed in a pre-specified manner as described in the protocol. In this study, AESI are listed below (as provided in the protocol), along with each AESI detailed definition: Treatment-emergent AESI (serious and nonserious) are flagged in the CRFs, defined as:

- Grade ≥ 2 infusion-related reactions up to day 4
- Grade ≥ 3 injection-site reactions up to day 4
- Grade ≥ 2 hypersensitivity reactions up to day 29
- Any treatment-emergent AE (TEAE) that led to a hospitalization or emergency room visit, regardless of whether the visit is related to COVID-19

4.6.3. Laboratory Safety Variables

The laboratory safety variables are blood chemistry and hematology. The tests for blood chemistry include: Sodium, Potassium, Chloride, Carbon Dioxide, Glucose, Blood urea nitrogen (BUN), Aspartate aminotransferase (AST), Alanine aminotransferase (ALT), Total bilirubin, Albumin, Alkaline phosphatase, Creatinine, Creatine phosphokinase (CPK), and Lactate dehydrogenase (LDH). Hematology tests include Hemoglobin, Hematocrit, Red blood cells (RBCs), White blood cells (WBCs), Platelet count, Differential Neutrophils, Lymphocytes, Monocytes, Basophils, and Eosinophils. Clinical laboratory values will be converted to standard international (SI) units and grouped by function in summary tables. Clinical laboratory values will be converted and analyzed in both standard international (SI) units and US conventional units provided by the central laboratory. Both actual test values and “change from baseline” values (defined as the post-baseline value minus the baseline value) over time will be summarized, where the post-baseline visits will

be assigned to the Global Analysis Windows. Potentially clinically significant values (PCSV) ranges will be applied to the laboratory test values as applicable (see PCSV criteria in [Appendix 11.2](#)).

4.6.4. Vital Signs

Vital signs (temperature, pulse, blood pressure, and respiration rate) will be summarized by baseline and change from baseline to each scheduled assessment time with descriptive statistics. Potentially clinically significant values (PCSV) ranges will be applied to corresponding vital sign parameter values according to (see PCSV criteria in [Appendix 11.2](#)).

4.7. Pharmacokinetic Variables and Anti-Drug Antibody (ADA) Variables

The pharmacokinetic (PK) variables are the concentration of REGN10933 and REGN10987 in serum and time. Samples are collected at the timepoints outlined in the Schedule of Events ([Appendix 11.1](#)).

4.8. Immunogenicity Variables

The immunogenicity variables are ADA response status, titer, NAb status, and time-point/visit. Samples for ADA analysis are collected at the timepoints outlined in the Schedule of Events ([Appendix 11.1](#)).

5. STATISTICAL METHODS

For continuous variables, descriptive statistics will include the following: the number of patients reflected in the calculation (n), mean, median, standard deviation, Q1, Q3, minimum, and maximum.

For categorical or ordinal data, frequencies and percentages will be displayed for each category.

Baseline is defined as the last assessment obtained before the first dose of study drug (i.e., either at screening or pre-dose assessment).

5.1. Demographics and Baseline Characteristics

Demographic and baseline characteristics will be summarized descriptively by treatment group and overall for the study. For viral load, there will be summaries and visualizations of key disease-related characteristics.

5.2. Medical History

Medical history will be summarized by SOC and PT and by treatment group and all groups combined in the SAF population.

5.3. Prior / Concomitant Medications

All prior medications, dictionary coded by WHODRUG (WHO Drug Global version 01MAR2020 B3), will be descriptively summarized by treatment group and overall for the study, for subjects in SAF population. All procedures, dictionary coded by MedDRA v23.1, will be summarized in the same fashion as prior/concomitant medications.

Summaries will present patient counts (and percentages) for all prior medications, by decreasing frequency of the overall group incidence of ATC followed by ATC level 2, ATC level 4 and preferred term. For prior procedure, summaries will be by SOC and PT, sorted by decreasing frequency of SOC and PT based on the incidence in the overall group incidence. Patients will be counted only once for each SOC and PT linked to the procedure.

All concomitant medications/procedures will be descriptively summarized by treatment group, for subjects in SAF.

5.4. Rescue / Prohibited Medications

Patients can receive rescue therapy for COVID-19 per local standard-of-care. Rescue treatment(s) will not be provided as part of the study. Listing of prohibited medications will be provided for patients in SAF.

5.5. Patient Disposition

Using the SAF, appropriate summaries of the patient disposition will be displayed. Summaries of total screened patients, numbers of each analysis set by treatment and total will be available. The following will be provided:

- The total number of screened patients: met the inclusion/exclusion criteria regarding the target indication and signed the ICF
- The total number of randomized patients: received a randomization number

- The total number of patients who discontinued the study, and the reasons for discontinuation
- The total number of patients who discontinued from study treatment, and the reasons for discontinuation
- A listing of patients treated but not randomized, patients randomized but not treated, and patients randomized but not treated as randomized
- A listing of patients prematurely discontinued from treatment, along with reasons for discontinuation

Using the SAF, summaries of discontinuation and/or dropouts by reasons and treatments will be presented.

5.6. Extent of Study Treatment Exposure and Compliance

This is a single dose study, with the site administering the doses. A listing will be provided of patients who are randomized but not dosed as well as infusions or injections that were either interrupted or not completed. Treatment compliance in terms of total dose and infusion interruption will be summarized by treatment group.

The extent of follow-up in the SAF population will be summarized. The numbers of patients completing 29 days and 169 days of follow-up will be tabulated.

The number and percentage of patients randomized and exposed to double-blind study drug, and duration of exposure to treatment during the study will be presented by treatment group.

5.7. Hypothesis Test

The statistical hypothesis for the primary virologic efficacy endpoint is:

H_0 : There is no difference between patients treated with one or more dose regimens of REGN10933+REGN10987 and patients treated with placebo in time weighted average daily change from baseline in viral load from day 1 to day 7

H_1 : REGN10933+REGN10987 reduces time weighted average daily change from baseline in viral load (\log_{10} copies/mL) from day 1 to day 7, relative to placebo

The type I error rate is 0.05.

[figure not shown]
5.7.1. Analysis of Primary Efficacy Variable

The primary virologic efficacy variable is the time-weighted average change from baseline in viral load from day 1 to day 7, as measured by RT-qPCR in NP swab samples. The primary analysis will be conducted in the Seronegative mFAS population. An Analysis of Covariance (ANCOVA) model with treatment group as a fixed effect and baseline viral load and treatment by baseline interaction as covariates will be fit to the data as the primary analysis. For efficacy analysis, the placebo IV and placebo SC arms are pooled.

A step-down testing approach will be used for comparing active treatment groups to the pooled placebo to control type I error rate at 0.05. The pairwise comparisons are performed using the t-

test. [Figure 2](#) below illustrates this hierarchy. If a test is insignificant, then the formal testing procedure stops at that step.

Figure 2: Testing Hierarchy

The least squares mean estimates and 95% confidence intervals for the TWA mean change from baseline in viral load will be presented for each treatment group, as well as for the difference between each REGN10933+REGN1097 treatment group and placebo along along with the p-values for the comparisons. Accompanying descriptive analyses will be provided at the individual timepoints used to calculate the TWA.

No hypothesis testing is planned for the between active dose comparisons. Only estimates and 95% confidence intervals will be reported for the between active dose comparisons.

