## 5. STUDY VARIABLES

### 5.1. Demographic and Baseline Characteristics

Baseline characteristics will include standard demography (eg, age, race, weight, height), disease characteristics (eg, baseline viral load [ $\log_{10}$  copies/mL, viral load threshold, and Ct], presence/absence of COVID-19-related symptoms, days since symptom onset), serology (negative, positive, or other), medical history, and medication history for each patient.

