#### 7.2.1. Inclusion Criteria

A patient must meet the following criteria to be eligible for inclusion in the study:

1. Is male or female  $\geq 18$  years of age (or country's legal age of adulthood) at randomization

*Note: upper age limit may apply; refer to other inclusion criteria.*

2. Has SARS-CoV-2-positive diagnostic test from a sample collected  $\leq 72$  hours prior to randomization, using a validated SARS-CoV-2 antigen, RT-PCR, or other molecular diagnostic assay and an appropriate sample such as nasopharyngeal (NP), nasal, oropharyngeal (OP), or saliva

*Note: Historical record of positive result is acceptable, as long as the sample was collected  $\leq 72$  hours prior to randomization.*

3. *Low-risk symptomatic patient:* Has symptoms consistent with COVID-19 (as determined by the investigator) with onset  $\leq 7$  days before randomization, and **meets all of the following 8 criteria:**

- a. Age  $\leq 50$
- b. No obesity, with obesity defined as BMI  $\geq 30$  kg/m^2
- c. Does not have cardiovascular disease or hypertension
- d. Does not have chronic lung disease or asthma
- e. Does not have type 1 or type 2 diabetes mellitus
- f. Does not have chronic kidney disease, with or without dialysis
- g. Does not have chronic liver disease
- h. Is not pregnant

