***or***

*Asymptomatic patient:* Has had no symptoms consistent with COVID-19 (as determined by the investigator) occurring at any time  $< 2$  months prior to randomization

4. Maintains O2 saturation  $\geq 93\%$  on room air
5. Is willing and able to provide informed consent signed by study patient or legally acceptable representative
6. Is willing and able to comply with study procedures, including providing samples for viral shedding testing

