### 11.4.3. Efficacy Analyses

#### 11.4.3.1. Primary Efficacy Analysis

The primary virologic efficacy variable is the time-weighted average change from baseline in viral load from day 1 to day 7, as measured by RT-qPCR in NP swab samples. The primary analysis will be conducted in the Seronegative mFAS population.

The analyses will be based on the observed data with no imputation for missing data. Viral load values less than the lower limit of quantification of the PCR assay but with positive qualitative results will be set to half of lower limit of quantification of the PCR assay; values with nondetectable RNA will be set to 0 log10 copies/mL if the reason for the negative value is not a failed test. Viral load values above the upper limit of quantification will be re-tested using the reflex test.

The primary efficacy variable will be calculated using the linear trapezoidal rule, ie, area under the curve for change from baseline at each time point from day 1 to last observation divided by the number of days from day 1 to day of last observation. The TWA estimates the average over the

time range of interest, adjusting for any irregular spacing of the timing when samples are taken (eg, if samples are missing).

An Analysis of Covariance (ANCOVA) model with treatment group as a fixed effect and baseline viral load and treatment by baseline interaction as covariates will be fit to the data as the primary analysis.

In addition, the least squares mean estimates for the TWA mean change from baseline in viral load will be presented for each treatment group, as well as for the difference between each REGN10933+REGN10987 treatment group and placebo as well as between active treatment groups. p-Values will be presented comparing the active arms to placebo. 95% confidence intervals will be reported between the active doses. Accompanying descriptive analyses will be provided at the individual time points used to calculate the TWA. To explore the dose response, other modeling approaches such as  $E_{\max}$  will be described in the SAP.

For efficacy analyses, the placebo IV and placebo SC arms are pooled.

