4. ANALYSIS VARIABLES

4.1. Demographic and Baseline Characteristics

Baseline characteristics will include standard demography (age, gender, race, and ethnicity), and baseline viral load measured with both \log_{10} copies/mL and Cycle Threshold (Ct), viral load threshold, presence/absence of COVID-19 related symptoms, serology (i.e., negative, positive, or other), medical history, and medication history for each patient.

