4.2. Medical History

Medical history includes (and may be include more such as risk factors)

- COVID-19 with start date as the date of onset of first symptoms related to COVID-19, as well as associated symptoms and their severity graded by NCI-CTCAE v5.0
- Whether the patient is receiving oxygen at home by nasal cannula
- Menopausal history
- Pregnancy or breastfeeding status, if applicable

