5.7.3. Subgroup Analyses

Subgroup analysis by gender, symptomatic vs. asymptomatic, race (white vs. other), and baseline viral load (above or below median) may be performed in seronegative mFAS in order to assess the consistency of results.

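### The primary ANCOVA leaves out symptom status and time since onset, which may cost modest precision, mainly in the between-dose confidence intervals

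*SAP*

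**What the plan says.** SAP 5.7.1 fits an ANCOVA to the TWA change in viral load with "treatment group as a fixed effect and baseline viral load and treatment by baseline interaction as covariates". Protocol 11.4.3.1 specifies the same model, so the two documents agree.

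Protocol 7.2.1 admits two kinds of patient. One "Has symptoms consistent with COVID-19 (as determined by the investigator) with onset" no more than 7 days before randomization. The other "Has had no symptoms consistent with COVID-19 (as determined by the investigator) occurring at any time" in the 2 months before randomization.

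Protocol 5.1 lists "presence/absence of COVID-19-related symptoms, days since symptom onset" among the baseline characteristics. SAP 4.1 keeps "presence/absence of COVID-19 related symptoms" but drops days since onset. The interval can still be derived, because SAP 4.2 collects "COVID-19 with start date as the date of onset of first symptoms related to COVID-19".

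In the efficacy analyses, symptom status appears only in SAP 5.7.3, as one of several optional subgroup factors. Time since onset appears in none. Protocol 8.6 and SAP 2.1 describe central randomization through an IWRS and name no stratification factor.

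**The concern.** The endpoint is the average change in viral load over a week, so it plausibly depends on where in the infection a patient stands at dosing. A given baseline load can be rising in one patient and falling in another, and baseline load alone cannot separate the two. Symptom status and days since onset might. Neither the primary analysis nor, as far as the documents say, the randomization takes account of them.

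What is at stake is interval width. SAP 2.1 gives the purpose as finding the lowest dose regimen whose virologic effect resembles that of 2400 mg IV. SAP 5.7.1 plans no tests between active doses, only estimates and 95% confidence intervals, so their width decides how much the trial can say about dose. SAP 2.2 planned 100 seronegative patients per group for these comparisons. The final analysis of the primary endpoint uses the first 816 patients, expected to give about 400 seronegative patients, or about 57 per group. Enrollment is closed, so covariate adjustment is one of the few remaining ways to narrow the intervals in that analysis.

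**Working it through.** **Inputs from the documents.** Difference 0.73 and SD 0.948 log10 copies/mL, 57 per group, and half-width 0.27 at 100 per group (SAP 2.2). Two-sided alpha 0.05 (protocol 11.4.4). Seven equal groups after the placebo arms are pooled (SAP 2.1).

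**Inputs assumed, because the documents give none.**
- 20% of patients are asymptomatic.
- The gap in TWA change between symptomatic and asymptomatic patients, adjusted for baseline viral load, is 0.3 to 0.8 log10.
- The slope is 0.05 to 0.15 log10 per day since onset within symptomatic patients, also adjusted.
- The SD of days since onset among symptomatic patients is 1.8 days.
- 0.948 is the residual SD of the current model.

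**Step 1: the plan's own figures.**
- Standard error = 0.948 × √(2/57) = 0.1776, and 0.73/0.1776 = 4.11.
- Power = Φ(4.11 − 1.96) = 98.4% (98.3% with the noncentral t). The stated figure of about 98% reproduces.
- Half-width at 100 per group = 1.96 × 0.948 × √(2/100) = 0.263, against a stated 0.27. This is close enough to be rounding or a slightly different SD.
- Half-width at 57 per group = 1.96 × 0.948 × √(2/57) = 0.348.

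**Step 2: share of residual variance explained.** The variance is 0.948² = 0.8987.
- Symptom status, p(1−p)d²/0.8987. Low: 0.16 × 0.09/0.8987 = 1.6%. High: 0.16 × 0.64/0.8987 = 11.4%.
- Days since onset. This varies only among the 80% who are symptomatic, so the share is 0.8 × (slope × 1.8)²/0.8987. Low: 0.8 × 0.0081/0.8987 = 0.7%. High: 0.8 × 0.0729/0.8987 = 6.5%.
- Sum: 2.3% to 17.9%. The shares add because one is between the two kinds of patient and the other is within the symptomatic.

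**Step 3: effect on precision at 57 per group.** The standard error and half-width scale by √(1−R²), and the equivalent sample size is 57/(1−R²).

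| | Current model | Low end | High end |
|---|---|---|---|
| R² | 0 | 2.3% | 17.9% |
| √(1−R²) | 1 | 0.988 | 0.906 |
| Half-width (log10) | 0.348 | 0.344 | 0.315 |
| SE reduction | none | 1.2% | 9.4% |
| Equivalent n per group | 57 | 58 | 69 |
| Power at 0.73 | 98.4% | 98.6% | 99.5% |

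The power row uses Φ(4.11/√(1−R²) − 1.96).

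**Step 4: smaller effects.** For an assumed true difference of 0.5 log10, power at 57 per group is 80% now. It becomes 82%, 84% or 88% at R² of 5%, 10% or 20%.

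**Step 5: cost.** Seven groups of 57 give 399 patients. The current model uses 14 parameters (seven intercepts and seven slopes), leaving 385 residual degrees of freedom. Two more terms break even at an R² of about 2/385 = 0.5%.

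**The case against.** The strongest reply is that nothing here is broken. The SAP follows the protocol, the model already includes the obvious predictor, and power at the planned difference hardly changes. That stands in full. A reader might infer from the omission that the primary comparison is biased, has the wrong type I error or is underpowered. The documents support none of these. Leaving a prognostic covariate out of a randomized comparison does not distort its expected value or its error rate, and the stated power reproduces.

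The benefit is also assumed. Every prognostic input above comes from outside the documents, and the range starts above zero. Baseline viral load may already carry much of the information. Eligibility also narrows the spread of infection stage: the qualifying sample must be at most 72 hours old, an earlier positive test excludes, and the primary set is seronegative. For asymptomatic patients the proposed coding says nothing about when infection began. All of this stands, so zero gain has to remain part of the answer.

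A reader might also infer that any prognostic term narrows every interval. That is too strong. A term must repay its degrees of freedom, and for a particular pair of arms that differ on the covariate, adjustment can widen the interval.

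Two further points qualify the stakes. Protocol 11.4.9 provides for later analyses beyond the first 816 patients, so 57 per group need not be the last word on dose comparisons. And 0.73 is a drug-versus-placebo effect, so it is not a yardstick for differences between doses.

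Finally, editing SAP 5.7.1 alone would be insufficient. The model is also written into the protocol, SAP 1.2.5 declares no departures from it, and SAP 7.3 has no rule for missing onset dates. The fix has to cover these.

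**Conclusion.** The point holds as an inexpensive improvement in efficiency. The plan collects two baseline variables that could predict the endpoint and uses neither in the primary model. Under the assumptions listed, adding them would reduce the standard error by about 1% to 9%, taking the half-width at 57 per group from 0.348 to between 0.344 and 0.315. The upper end needs a large gap and a steep slope together. If neither term is prognostic once baseline viral load is in the model, there is no gain and the loss is 2 of about 385 degrees of freedom. The benefit would fall mainly on the between-dose intervals and on any true difference from placebo well below 0.73.

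**What to change.** Before unblinding:

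- In SAP 5.7.1, add two main effects to the primary ANCOVA: symptom status at baseline (yes/no), and days since symptom onset. Set days to a constant such as 0 for asymptomatic patients. With the status indicator in the model, the choice of constant does not affect the treatment contrasts.
- Use the same two terms in the day 1 to 5 TWA ANCOVA and in the MMRM (SAP 5.7.5).
- In SAP 7.3, state a rule for missing or partial onset dates, applied without reference to treatment, so that no patient drops out of the model.
- Add days since onset to the baseline variables in SAP 4.1, as protocol 5.1 already has it.
- Record the departure from the protocol model in SAP 1.2.5, or amend protocol 11.4.3 to match.

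The cost is 2 degrees of freedom and a few lines of text. No new data are needed.

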5.7.2. Analysis in Patients with High Viral Loads

Within the Overall mFAS population, analysis of the change from baseline in viral load at each visit will be performed in baseline viral load categories ($>10^4$ copies/mL, $>10^5$ copies/mL, $>10^6$ copies/mL, $>10^7$ copies/mL) using the same method as described above using ANCOVA.

